- The investigator must contact the Pfizer study physician immediately in the event of a subject's experiencing an MAE or SAE during the active safety period (Day 1 to Day 7). See Section 7.9 Stopping Rules for further detail on safety reporting requirements for sentinel-cohort subjects. All AEs should be promptly captured in the CRF and/or SAE reports as applicable (see Section 8 Safety for reporting requirements).

6.1.2. Visit 2 (Week 1), Follow-up Visit (7 to 10 Days After Visit 1)

• Confirm that the subject continues to be eligible for the study and does not meet any withdrawal criteria (Section 6.4).

- Record nonstudy vaccinations.
- Review the subject's e-diary data and follow up on any ongoing reactogenicity or use of antipyretic medication.
- Collect the e-diary.
- Using the study visit AE checklist as a guide:
 - Inquire whether the subject had any NDCMCs since the last visit. Inquire whether the subject had any of the following related to an AE since the last visit: hospitalizations, visits to other medical facilities, and medication use. Please refer to the SRM for additional details.
 - Inquire about neuroinflammatory conditions and autoimmune conditions, such as transverse myelitis, uveitis, optic neuritis, and multiple sclerosis. Please refer to the SRM for additional details
 - ➤ Record AEs as described in the AE reporting section (Section 8) and the Schedule of Activities. The time of onset will be recorded for any AE that occurs on the same day as investigational product administration.
 - Review AEs that were ongoing from the previous visit and record their end dates or confirm that they are still ongoing.
- Record concomitant medications used to treat AEs (see Section 5.7 and Section 7.6.4).
- Ask the subject's parent(s)/legal guardian to contact the investigator immediately if any illness requiring medical attention or hospitalization occurs between visits.
- Notify the subject's parent(s)/legal guardian that he or she will receive a phone call (Visit 3) in approximately 3 weeks (25 to 35 days after Visit 1) to follow up on the child's health, any ongoing AEs, and new concomitant medications and nonstudy vaccinations.
- Schedule an appointment for the next study visit within the time window per protocol.

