- Confirm the subject's next clinic appointment.
- Complete the source documents and the CRF.

Final Protocol Amendment 2, 19 April 2016

6.1.4. Visit 4 (Month 2), Vaccination 2 (42 to 70 Days After Visit 1)

Note that any sentinel subject who has been withdrawn from the study on IRC/external data monitoring committee (EDMC) recommendations will complete a modified Visit 4. Procedures to be followed are detailed in Section 6.1.11.

Visit 4 must not be performed on any sentinel subject until the IRC has completed the post-Vaccination 1 safety review (specific to the subject's sentinel cohort) and has given its recommendations to proceed with the study. For sentinel-cohort subjects who are unable to receive Vaccination 2 within the protocol-specified window because of availability of the IRC recommendation, the visit window may be extended for individual subjects by up to 14 days from the receipt of the positive IRC recommendation, at the discretion of the sponsor.

- Ensure that the subject continues to be eligible for the study and meets none of the withdrawal or temporary delay criteria (Section 4.3, Section 4.4, and Section 6.4). In the case where temporary delay criteria are met, all assessments and procedures noted below should be delayed, reperformed, or reconfirmed, as applicable, on the rescheduled date of vaccination.
- Perform a brief physical examination comprising general appearance, ears, throat, heart, and lungs.
- On the day of and prior to vaccination, measure and record in the source document the subject's axillary temperature, heart rate, and respiratory rate. Record the route by which the temperature was taken.
- Record nonstudy vaccinations.
- The unblinded administrator administers a single intramuscular injection of investigational product (bivalent rLP2086 or saline) into the deltoid muscle or anterolateral thigh muscle. Kit number, site of administration, and time of administration are recorded for CRF entry.
- Following investigational product administration, the blinded observer will observe the subject for at least 30 minutes (or longer as per local practice) for any acute reactions. Any events observed within 30 minutes after vaccine administration will be recorded as immediate AEs on the AE CRF. Date and time of vaccination and date and time of onset of the event will be captured in the CRFs.
- Using the study visit AE checklist as a guide:

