 - Review AEs that were ongoing from the previous visit and record their end dates or confirm that they are still ongoing.

- Record concomitant medications used to treat AEs (see Section 5.7 and Section 7.6.4).
- Ask the subject's parent(s)/legal guardian to contact the investigator immediately if any significant illness or hospitalization occurs between visits.
- Remind the subject's parent(s)/legal guardian that nonstudy vaccinations should not be administered within a 28-day window (live vaccines) or 14-day window (nonlive vaccines or intramuscular/sublingual allergen immunotherapy) either before or after a study vaccine administration.
- Schedule an appointment for the next study visit within the time window per protocol.
- Complete the source documents and CRF.

Between visits, contact the subject's parent(s)/legal guardian in order to obtain stop dates for any local reactions, systemic events, or use of antipyretic medication that was ongoing on the last day that the e-diary was completed. The stop dates should be documented in the source documents and the information should be entered into the CRF.

6.1.6. Visit 6 (Month 6), Vaccination 3 (105 to 126 Days After Visit 4)

- Ensure that the subject continues to be eligible for the study and meets none of the withdrawal or temporary delay criteria (Section 4.3, Section 4.4, and Section 6.4). In the case where temporary delay criteria are met, all assessments and procedures noted below should be delayed, reperformed, or reconfirmed, as applicable, on the rescheduled date of vaccination.
- Perform a brief physical examination comprising general appearance, ears, throat, heart, and lungs.
- On the day of and prior to vaccination, measure and record in the source the subject's axillary temperature, heart rate, and respiratory rate. Record the route by which the temperature was taken.
- Record nonstudy vaccinations.
- The unblinded administrator administers a single intramuscular injection of investigational product (bivalent rLP2086 or HAV vaccine) into the deltoid muscle or anterolateral thigh muscle. Kit number, site of administration, and time of administration are recorded for CRF entry.

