- If the reaction exceeds the maximum size the caliper is able to measure (>14 caliper units, Section 7.4.1), the parent(s)/legal guardian should also use the measuring tape to measure the maximum diameter of redness and/or swelling at the injection site, and report this immediately to the investigator.
- Ask the parent(s)/legal guardian to report the maximum diameter of the redness and/or swelling at the injection site to the investigator daily until the reaction becomes ≤14 caliper units.

- Ask the subject's parent(s)/legal guardian to contact the investigator immediately if any significant illness or hospitalization occurs.
- Remind the subject's parent(s)/legal guardian that nonstudy vaccinations should not be administered within a 28-day window (live vaccines) or 14-day window (nonlive vaccines or intramuscular/sublingual allergen immunotherapy) before or after a study vaccine administration.
- Schedule an appointment for the next study visit and confirm that it is scheduled within the time window per protocol.
- Remind the subject's parent(s)/legal guardian to bring the e-diary to the next study visit.
- Complete the source documents.
- Complete the CRF and update the investigational product accountability records.

Between visits, review the e-diary data online at frequent intervals. Contact the parent(s)/legal guardian in order to obtain stop dates for any local reactions, systemic events, or use of antipyretic medication that was ongoing on the last day that the e-diary was completed. The stop dates should be documented in the source documents and the information should be entered into the CRF at the next study visit of the subject.

6.1.7. Visit 7 (Month 7) (28 to 42 Days after Visit 6) Blood Collection

- Confirm that the subject continues to be eligible for the study and meets none of the withdrawal criteria (Section 6.4) and none of the temporary delay criteria for the blood draw (Section 4.4).
- Obtain a 5-mL blood sample. Local anesthetic may be applied prior to the blood draw.
- Record nonstudy vaccinations.
- Review the subject's e-diary data and follow up on any ongoing reactogenicity or use of antipyretic medication.
- Collect the e-diary.
- Using the study visit AE checklist as a guide:

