8.2.5.2.7. Multiple Events per Subject (Incidence Rates)

The frequency distribution on number of events reported by each subject will be summarized for each of the following safety variables:

1. Any AE during the vaccination phase.
2. Any SAE throughout the AE collection period (Visit 1 to Visit 8),
3. Any medically attended AE throughout the AE collection period (Visit 1 to Visit 8).
4. Any newly diagnosed chronic medical conditions throughout the AE collection period (Visit 1 to Visit 8).
5. Any newly diagnosed chronic medical conditions categorized as throughout the AE collection period (Visit 1 to Visit 8).

For each subject, the number of events reported per year will be estimated by summarizing the total number of events reported over the observation period and standardizing it to an annual rate by multiplying by 365 and dividing by days on study. The overall incidence rate (including 95% confidence intervals) for each of the safety variables will be reported by group.

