10.1.5.6.2. Dates

The 2 dates will be used to derive total subject-duration for the calculation of incidence rates.

2 subject summary pages will be provided (one for end of vaccination phase and one for end of study); therefore the 2 dates can be derived from the 2 pages.

Table 13. End of Study Date and End of Vaccination Phase Date

Study	# of Subject Summary Page	End of Vaccination Date	End of Study Date
B1971035	2	
 Visit Date for ‘Subject summary Page- Vaccination Phase’ (This date should be on the same day of last visit during vaccination phase or later) 	
 Visit Date for ‘Subject summary Page- End of Study’ (This date should either be the Visit 10 or Visit 13 date, whichever is later)

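### The SAP never says how the group incidence rate or its CI is formed: one section annualises per child, another points to total time, and that time runs past the end of event counting

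*SAP*

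**What the plan says.** SAP 8.2.5.2.7 covers AEs in the vaccination phase and SAEs, medically attended AEs and NDCMCs from Visit 1 to Visit 8. For each child it annualises the event count by "standardizing it to an annual rate by multiplying by 365 and dividing by days on study". The next sentence is the only one on the group figure: "The overall incidence rate (including 95% confidence intervals) for each of the safety variables will be reported by group". It does not say how child-level values become a group value, or how the interval is computed.

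SAP 10.1.5.6.2 takes an end-of-vaccination date and an end-of-study date from the subject summary pages and states: "The 2 dates will be used to derive total subject-duration for the calculation of incidence rates". Its Table 13 says of the end-of-study date: "This date should either be the Visit 10 or Visit 13 date, whichever is later".

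Two other places fix the event windows. SAP Table 8 stops SAE, MAE and NDCMC counting at Visit 8. SAP Table 11 stops the vaccination phase at the post-Vaccination 3 blood draw, or at withdrawal for children who leave early.

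**The concern.** Both sections bear on the same output, but they suggest different calculations. A programmer working from 8.2.5.2.7 could reasonably average the per-child annual rates. One working from the appendix would divide total events by total time. When every child has similar follow-up, the two nearly agree. They separate when a child with an event leaves early, because the average gives a few days of follow-up the same weight as seven months.

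The time wording raises a second problem that affects both estimators. If the denominator runs to the end-of-study date, it includes time in which SAEs, MAEs and NDCMCs are no longer counted. Only rLP2086 children enter Stage 2, so that surplus time is much longer in the vaccine groups.

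Safety against control is a primary objective, and SAP 8.1.2.2 uses safety intervals to pick out events for further clinical investigation. A rate that depends on the programmer's reading, or on unequal surplus time, is a poor input to that judgement.

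**Working it through.** The documents state no incidence rate, so there is no figure to reproduce. The check compares the two readings.

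**Inputs from the documents**
- Vaccination phase, from the Visit 4, 6 and 7 windows: 42+105+28 = 175 days to 70+126+42 = 238 days. I use 206, close to the midpoint.
- Visit 1 to Visit 8: 42+105+168 = 315 to 70+126+196 = 392 days. I use about 350.
- Visit 1 to Visit 9, which Visit 10 follows: 42+105+337 = 484 to 70+126+365 = 561 days. I use about 520 for Visit 10.
- Visit 13 is at Month 54: about 1,640 days.
- Group sizes per age stratum, from 33 + 33 sentinel and 132 expanded children at 2:1: 22 on a non-selected dose and 66 controls. Over both strata: up to 132 controls and up to 264 rLP2086 children.

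**Assumptions (not in the documents)**
- Each completer has 2 AEs over 206 days (range 1 to 4).
- One child leaves at day 8 (or day 30) with 1 AE.

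**One child's rate**, 365 x events / days, for 1 event: 365/8 = 45.6 per year; 365/10 = 36.5; 365/30 = 12.2; 365/206 = 1.77.

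**Two group estimators**
- (a) Mean of child rates: [(n−1) x 365 x 2/206 + 365/8] / n
- (b) Person-time: 365 x [2(n−1) + 1] / [206(n−1) + 8]

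At n=66:
- (a) = (65 x 3.544 + 45.6)/66 = 4.18
- (b) = 365 x 131/13,398 = 3.57

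| n | (a) | (b) | Excess, day 8 | Excess, day 30 |
|---|---|---|---|---|
| 22 | 5.46 | 3.62 | +51% | +9% |
| 66 | 4.18 | 3.57 | +17% | +3% |
| 132 | 3.86 | 3.56 | +9% | +2% |
| 264 | 3.70 | 3.55 | +4% | +1% |

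Columns (a) and (b) are for the day-8 leaver. The day-8 excess also depends on the assumed AE rate. With 1 AE per completer it is about +36% at n=66 and +9% at n=264; with 4 AEs it is +8% and +2%.

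**Rare events.** Assume about 2% of children have one SAE over 350 days, plus one SAE in a child who leaves at day 8. At n=66:
- (a) = (365/350 + 365/8)/66 = 0.707
- (b) = 365 x 2/(350 x 65 + 8) = 0.032, so (a) is about 22 times (b).

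The ratio is about 12 at n=132 and 8 at n=264. If that child's days run instead to a contact at about 180 days, the ratios fall to about 1.5, 1.2 and 1.2.

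**Surplus time.** One SAE in a child followed throughout gives:
- to Visit 8: 365/350 = 1.04 per year
- to Visit 10 (control): 365/520 = 0.70
- to Visit 13 (rLP2086 in Stage 2): 365/1,640 = 0.22

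With equal true rates, the control rate is multiplied by 350/520 = 0.67. The rate in rLP2086 children who complete Stage 2 is multiplied by 350/1,640 = 0.21. Their ratio would be about 520/1,640 = 0.32 instead of 1.

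**The case against.** A reader might infer that the SAP's stated method is to average per-child rates, and that the bias is therefore built in. The documents do not support that. SAP 8.2.5.2.7 contains no averaging instruction, and 10.1.5.6.2 uses person-time language. If the appendix governs, the early leaver adds one event and a few days, and the over-weighting does not arise.

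A reader might also infer that early leavers dominate the average and drive its interval. At n=66 the day-8 leaver supplies 45.6/66 = 0.69 of 4.18, about 17%. At n=22 it is 45.6/22 = 2.07 of 5.46, about 38%. Neither is dominance, and nothing can be said about the interval because no CI method is named.

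Early leavers are also partly covered. Protocol 6.1.12 plans a safety call about six months after the last dose for children who withdraw before Visit 8. If that time counts, one event is about 365/180 = 2.0 per year. This could help the SAE, MAE and NDCMC rates, although the SAP does not say that it counts. It does not help the AE rate, because Table 11 closes that interval at withdrawal.

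The impact is limited. The primary safety endpoints are percentages of children, the vaccine-control comparisons use proportions, and no between-group test of these rates is planned.

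The surplus-time figures assume that the end-of-study date serves as the denominator for the Visit 8 endpoints, which is a natural reading but not an explicit one. At the primary analysis many children would not yet have that date. That limits the dilution then, but leaves the denominator undefined.

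**Conclusion.** The point holds as an unresolved specification. The SAP gives a per-child formula in one place and a total-time denominator in another, with no group formula and no CI method. The difference can matter in small displayed groups with a very early leaver: +51% at n=22 and +17% at n=66 under the assumptions above. It shrinks to +4% at n=264, and to 1% to 3% for n=66 to 264 when the child leaves at day 30. AE, SAE and withdrawal rates are assumed throughout.

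Choosing total time settles the weighting but is not enough on its own. The time must also stop where event counting stops; otherwise the rLP2086 rates for SAEs, MAEs and NDCMCs are diluted more than the control rates. Severity is minor, because these summaries are descriptive and supplement the percentage-of-subjects endpoints.

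**What to change.** In SAP 8.2.5.2.7:
- Define the group rate as 365 x total events in the window / total days observed in that same window.
- State the windows: Visit 1 to Visit 7 or withdrawal for AEs; Visit 1 to Visit 8 or last safety contact for SAEs, MAEs and NDCMCs.
- Drop the per-child annual rate as the basis for the group figure. The planned frequency distribution of events per child can stay.
- Name a 95% CI that allows for repeated events within a child, for example a subject-level bootstrap or a negative binomial model with a log-time offset. Use an exact Poisson interval when events are very few, since a negative binomial fit may then be unstable.

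Align 10.1.5.6.2 so that its dates are truncated to these windows. The cost is about two sentences in 8.2.5.2.7, a matching edit in the appendix and a small programming change. No new data are needed.

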8.2.5.3. AEs and any RRI Occurring Within 48 Hours After Blood Draw

From Visit 8 to Visit 13 AEs and research-related injuries (RRI) occurring within 48 hours of a blood draw will be collected. A medically important RRI is any untoward medical occurrence that, results in death, is life-threatening (immediate risk of death), requires inpatient hospitalization or prolongation of existing hospitalization, results in persistent or significant disability/incapacity, results in congenital anomaly/birth defect. Medical and scientific judgment is exercised in determining whether an injury is an important medical event. AEs and RRIs occurring within 48 hours of a blood draw will be listed in the CSR. Events with an onset equal to the date of Visit 8 will be reviewed by the study lead clinician; unless otherwise documented before the database release, any events with an onset equal to the date of Visit 8 will be included on the appropriate listing(s) of AEs and RRIs.

8.2.5.4. Death

Any death data will be listed.

8.2.6. Analyses of Study Conduct

8.2.6.1. Subject Disposition, Vaccination Administration, Blood Samples

The number and percentage of subjects who are randomized, take each dose of investigational product, withdrew during the vaccination phase, completed the vaccination phase, completed and withdrew in the follow-up phase in stage 1, entered stage 2 and completed stage 2, and are major protocol violators and are major protocol violators (excluded from evaluable immunogenicity population at 1 month following vaccination 3), will be summarized. The reasons for withdrawal will also be tabulated.

In addition, the relationship of randomized vaccine group to actual vaccine received will be presented as a cross tabulation of the actual sequence received versus the randomized vaccine administration regimen.

For each blood draw, the number and percentage of subjects randomized, vaccinated (visits 1, 4, 6), and providing blood samples within the protocol-specified time frame, as well as before and after the specified time frame, will be tabulated.

Similarly, for each vaccination visit, the number and percentage of subjects who are enrolled, vaccinated (visits 1, 4, 6), and vaccinated within the protocol-specified time frame, before and after the specified time frame will be tabulated.

The number and percentage of subjects included in each analysis population will be summarized.

The ITT population will be used to generate these tables. All of the summary tables will be presented for each randomized group and total population.

A listing of subjects' non-compliant vaccine administration will be provided. The protocol violators will also be listed. Subjects receive the vaccine not as randomized will be listed as well. A listing of subjects that withdrew and subjects who withdrew due to AEs will be provided.

Listings for the subjects with flags to be included or excluded in each analysis population will be provided. The reason for not including a subject in a specific analysis population will be listed.

8.2.6.2. Demographic, Medical History, and Baseline Characteristics

Standard summary reports will be provided. Demographic summaries may also be generated for different analysis sets as defined in [Section 5](#).

8.2.6.3. E-Diary Completion

Variables defined in [Section 6.3.1](#) will be summarized for each group using descriptive statistics. The denominator for the e-Diary compliance rates will be the total number of subjects who receive the vaccination.

8.2.6.4. Nonstudy Vaccination

Nonstudy vaccination summaries will be provided for the following analysis intervals: prior to the vaccination and during the vaccination phase. The denominator for the percentages will be the safety population.

8.2.7. Subgroup Analysis

Some immunogenicity and safety endpoints will be descriptively summarized by race, by gender, and by country, and within age strata as described in [Section 6.4](#).

All of the safety and immunogenicity analyses will be summarized for each age stratum separately as well as for the overall populations. Note that for both the immunogenicity and the safety summaries, the summaries combining age cohorts will only be provided if the same dose-level is chosen for the expanded enrolment for each cohort. For example, if the low dose is chosen in the 12-18 months old age cohort and the high dose is chosen for the 18-24 months old age cohort, then the safety and immunogenicity results for the 12-24 months old group combined will not be presented. If there are no events for a specific safety analysis for the combined age strata, summaries by each age strata may not be performed.

For the safety endpoints (AE, SAE collected, medically attended AE and newly diagnosed chronic medical conditions) collected, a separate summary table including analysis interval of 'Vaccination period', 'Follow-up Phase (Stage 1)' (excluding AEs) and 'Throughout the AE collection period' (excluding AEs), will be provided for the subjects who completed the full series (3 doses) and those who only completed partial series (1 or 2 doses). Similar subgroup analysis will also be provided for those safety endpoints with relatedness of vaccination phase.

All of the p-values and 95% CI provided for the subgroup analyses are considered as descriptive and no multiplicity adjustment will be made on these analyses. No formal inferences will be made between the subgroups.

